SPONSOR: Merck, Sharp & Dohme Corp.

TITLE: A single arm Phase I/II study of MK-3475 combined with vorinostat for recurrent unresectable and/or metastatic squamous cell head and neck cancer and recurrent unresectable and/or metastatic salivary gland malignancies

IND NUMBER: IND exempt

Fred Hutchinson Cancer Research Center Protocol ID: 9383

Principal Investigator: [name] University of Washington [name] [contact] [contact] Email: [contact]

Sub-Investigators: [name], MPH [name] [name] [name] [name] [name] [name] [name] [name] [name]

Abbreviated Title	MK-3475 and vorinostat in head and neck cancer		
Trial Phase	Phase I/II		
Clinical Indication	Recurrent/Metastatic squamous cell head and neck carcinoma and salivary gland cancer		
Trial Type	Open label single arm study		
Type of control	None		
Route of administration	IV (MK-3475) and oral (Vorinostat)		
Trial Blinding	None		
Treatment Groups	Single Arm Combination study		
Number of trial subjects	Cohort 1 (squamous cell carcinoma) =35 Cohort 2 (salivary gland cancer) =35		
Estimated duration of trial	24 months		
Duration of Participation	24 months maximum for each patient		

1.0 TRIAL SUMMARY

1.1 INDICATION

COHORT 1 Recurrent unresectable and/or metastatic squamous cell carcinomas of the head and neck (RMHNSCC)

COHORT 2 Recurrent unresectable and/or metastatic salivary gland carcinomas (RMSGC)

2.0 TRIAL DESIGN

2.1 Trial Design

This study is an open label, single arm study which will enroll in patients with RMHNSCC and RMSGC. Positive tumor PDL1 expression by IHC will not be required for enrollment.

All patients with receive MK-3475 and vorinostat in combination. Vorinostat will be started on the same day as the initiation of MK-475 200 mg flat dose given Q21 days and continued through the 21 day cycle. Vorinostat will be given 5 out of 7 days at a dose of 400mg QD.

Vorinostat and MK-3475 have well defined toxicities as single agents and have nonoverlapping mechanisms of action. The safety of the two agents used in combination has not been previously described; therefore the study will be conducted in a phase I/II design.

2.1.1 Phase I run in

Both drugs are FDA approved for other disease indications, with safety and tolerability well described at the approved doses. Therefore the limited phase I portion of this study aims to

assess the safety and tolerability of this drug combination at their established doses. There will be no dose escalation cohorts within this phase I run in group.

The first six patients will constitute the phase I portion of this study. These initial 6 patients may come from either cohort and will be assessed for dose limiting toxicities (DLTs, defined in Section 2.1.1.1) after completion of cycle #1. After these first 6 patients initiate cycle #1, enrollment to the study will be temporarily halted, and a formal DLT evaluation of all 6 patients will be conducted.

If ≤ 2 of these six patients experience DLTs after completion of cycle #1, then the study will proceed to the phase II portion, using MK-3475 200mg IV Q21 days and Vorinostat 400mg PO 5 out of 7 days (x 3 weeks) of each 21 day cycle.

If > 2 of these first 6 patients experience a DLT upon completion of cycle #1, the study will proceed to the phase II portion using MK-3475 IV 200mg Q28 days Vorinostat 300mg daily 5 out of 7 days (x 4 weeks) of each 28 day cycle.

Only upon completion of the DLT evaluation for these first 6 patients and the determination of appropriate Phase II dose, will enrollment reopen for the phase II expansion.

2.1.1.1 Definition of Dose-Limiting Toxicities

All toxicities will be graded using National Cancer Institute (NCI) CTCAE Version 4.0 (see Appendix).

The occurrence of any of the following toxicities during Cycle 1 will be considered a DLT, if judged by the Investigator to be possibly, probably or definitely related to study drug administration:

- 1. Grade 4 non-hematologic toxicity (not laboratory)
- 2. Grade 3 non-hematologic toxicity (not laboratory) lasting >3 days despite optimal supportive care.
- 3. Any Grade 3 or Grade 4 non-hematologic laboratory value if:
 - Medical intervention is required to treat the patient, or
 - The abnormality leads to hospitalization
- 4. Grade 3 or Grade 4 febrile neutropenia:
 - Grade 3 is defined as ANC <1000/mm3 with a single temperature of >38.3 degrees C (101 degrees F) or a sustained temperature of ≥38 degrees C (100.4 degrees F) for more than one hour
 - Grade 4 is defined as ANC <1000/mm3 with a single temperature of
- >38.3 degrees C (101 degrees F) or a sustained temperature of \ge 38 degrees C (100.4

degrees F) for more than one hour, with life-threatening consequences and urgent intervention indicated.

5. Prolonged delay (>2 weeks) in initiating cycle 2 due to treatment-related toxicity

- 6. Hematologic toxicity requiring dose modifications as outlined in Section 5.1.2.4
 - 7. Grade 5 toxicity.

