2.1.2. Phase II expansion

After the first 6 patients have been assessed for DLTs upon completion of cycle 1 of treatment, and the appropriate vorinostat dose and MK-3475 dosing interval determined for phase II expansion, additional patients will be enrolled with RMHNSCC (Cohort 1) and RMSCG (Cohort 2) to total 35 patients in each cohort. Patients enrolled in the phase I and II portions will be used to assess the safety and efficacy outcomes of interest in each cohort.

Patients will be evaluated every 9 weeks $(63 \pm 7 \text{ days})$ with radiographic imaging to assess response to treatment. All imaging will be assessed using Response Evaluation Criteria in Solid Tumors (RECIST) 1.1 Patients will also be assessed by immune response criteria (IrRC – Appendix) for determination of overall response rate (ORR) and progression-free survival (PFS). Adverse events will be monitored throughout the trial and graded in severity according to the guidelines outlined in the NCI Common Terminology Criteria for Adverse Events (CTCAE) version 4.0.

Treatment with MK-3475 and vorinostat will continue until two years of therapy have been administered, or until

- 1. Documented disease progression (investigators may elect to continue MK-3475 treatment beyond progression in specific circumstances, unacceptable adverse event(s)
- 2. Intercurrent illness that prevents further administration of treatment
- 3. Investigator's decision to withdraw the subject
- 4. Subject withdraws consent,
- 5. Pregnancy of the subject,
- 6. Non-compliance with trial treatment or procedure requirements, or administrative reasons.

MK-3475 and vorinostat treated subjects who attain an investigator-determined confirmed complete response (CR) per RECIST 1.1 and IrRC may consider stopping trial treatment. Patients with a CR may continue on therapy for up to 2 cycles until a confirmatory scan is undertaken. If patients upon a confirmed CR progress they may continue therapy on a second course of therapy the combination until toxicity, progression. These subjects will be eligible for re-treatment for up to one year with MK-3475 and vorinostat after they have experienced radiographic disease progression at the discretion of the investigator according to the criteria in Section 5.1.4; this re-treatment will be the Second Course Phase. Response or progression in the Second Course Phase will not count towards the ORR and PFS of the primary endpoint in this trial.

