- A new course of treatment may begin on the scheduled Day 1 of a new cycle if all non-hematological toxicity from the previous cycle has recovered to ≤ Grade 1 or baseline, and/or hematologic recovery documented as outlined in section 5.2.1.4.

Initiation of subsequent cycles of therapy may be delayed for up to 12 weeks to allow recovery from all drug-related toxicity. Alternately, the Investigator may choose to administer supportive care (blood product transfusions) for retreatment criteria to be met. If the recovery criteria are not met after a 12-week delay, the patient will be discontinued from study treatment unless, in the opinion of the Investigator, the patient is experiencing a clinical benefit, in which case a decision regarding continuation of treatment will be made on an individual patient basis in consultation with the Merck medical monitor. Justification will be recorded in the source documents.

When initiating a subsequent cycle, a minimum interval of 21 days should be observed between MK-3475 administrations (with no minimum interval for vorinostat).

Continuation of study therapy during a cycle:

Within any cycle, the dose/schedule of either study drug may be adjusted as necessary.

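### The run-in counts DLTs only within cycle 1 and is decided on its completion, but one listed DLT, a cycle 2 delay of more than 2 weeks, cannot be met until about day 37

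*Combined protocol and SAP*

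**What the plan says.** Section 2.1.1 has the first six patients start cycle 1, halts enrolment, and states that they "will be assessed for dose limiting toxicities (DLTs, defined in Section 2.1.1.1) after completion of cycle #1". The result picks the phase II regimen. The starting regimen is kept under this condition: "If ≤ 2 of these six patients experience DLTs after completion of cycle #1, then the study will proceed to the phase II portion". The alternative regimen follows under this one: "If > 2 of these first 6 patients experience a DLT upon completion of cycle #1". Enrolment stays closed meanwhile: "Only upon completion of the DLT evaluation for these first 6 patients and the determination of appropriate Phase II dose, will enrollment reopen". Section 2.1.2 repeats the timing: "After the first 6 patients have been assessed for DLTs upon completion of cycle 1 of treatment".

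Section 2.1.1.1 sets the window: "The occurrence of any of the following toxicities during Cycle 1 will be considered a DLT", provided the investigator judges it at least possibly related. The fifth of its seven criteria is "Prolonged delay (>2 weeks) in initiating cycle 2 due to treatment-related toxicity".

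Section 2.1 fixes the cycle at 21 days. Section 5.2.1.5 requires at least 21 days between MK-3475 doses, lets a later cycle be delayed by up to 12 weeks, and allows a new cycle to begin "if all non-hematological toxicity from the previous cycle has recovered to ≤ Grade 1 or baseline".

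**The concern.** The window closes with cycle 1, but criterion 5 describes something that happens afterwards. Nothing elsewhere in the document reconciles the two. No section extends the observation period, makes the evaluation wait for cycle 2, or says how to count a patient whose cycle 2 is pending. The replacement rule in section 5.9 covers only patients who received less than 90% of the first infusion and had no DLT.

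The six-patient count is the only numerical safety rule in the plan. It selects the regimen for up to 64 further patients (35 + 35 − 6). Leaving out a listed DLT can lower the count but never raise it, so any error leans towards the starting regimen.

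**Working it through.** **Plan's own figure.** The plan states no operating characteristic for the six-patient rule, so there is nothing to reproduce.

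**When criterion 5 can be met.** Inputs: 21-day cycle (2.1), 21-day minimum interval (5.2.1.5), delay of more than 14 days (2.1.1.1).
- Cycle 2 due: day 1 + 21 = day 22.
- Exactly two weeks late: day 22 + 14 = day 36.
- First day more than two weeks late: day 37, which is 16 days after day 21.
- Counted from a 3-day administrative shift later (5.2.2): day 40. A shift 3 days earlier would give day 34, but dosing early conflicts with the 21-day minimum.

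Criterion 5 therefore cannot occur during cycle 1 on any of these counts.

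**Whether criterion 5 adds anything.** It would be redundant if every toxicity that holds cycle 2 already met another criterion. That is not so:
- A Grade 3 or 4 laboratory value needing neither intervention nor hospitalization falls outside criterion 3, but section 5.2.1.2 generally holds both drugs for Grade 3 or 4 toxicity until recovery.
- A Grade 3 non-hematologic event that falls to Grade 2 within 3 days and stays there escapes criterion 2, but has not recovered to Grade 1 or baseline.
- Persistent related Grade 2 toxicity meets none of criteria 1 to 4. Whether it holds cycle 2 depends on the section read. The recovery condition in 5.2.1.5 implies that it does. Section 5.2.1.2 requires only Grade 3 or 4 toxicity to resolve, and its modification table makes withholding at Grade 2 a matter for consideration and treats Grade 2 fatigue and alopecia like Grade 1.

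**Effect on the decision.** Let p be the chance of a DLT by the other criteria, q the chance of a DLT by criterion 5 only, and k the number of the six patients in whom criterion 5 cannot be scored. The counted total is X = Binomial(k, p) + Binomial(6 − k, p + q), and the starting regimen is kept if X ≤ 2. The values of p and q are assumptions.

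For p = 0.25, q = 0.15:
- k = 0: Binomial(6, 0.40) gives 0.0467 + 0.1866 + 0.3110 = 0.544.
- k = 1: 0.75 × P(Binomial(5, 0.40) ≤ 2) + 0.25 × P(Binomial(5, 0.40) ≤ 1) = 0.75 × 0.6826 + 0.25 × 0.3370 = 0.596.
- k = 6: Binomial(6, 0.25) gives 0.1780 + 0.3560 + 0.2966 = 0.831.

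Chance of keeping the starting regimen, P(X ≤ 2):

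| Assumed p + q | All counted (k = 0) | k = 1 | k = 2 | Worst case (k = 6) |
|---|---|---|---|---|
| 25% + 15% | 54% | 60% | 65% | 83% |
| 25% + 10% | 65% | 68% | 71% | 83% |
| 20% + 5% | 83% | 84% | 86% | 90% |

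**Which k applies.** If the in-cycle-1 wording is followed literally, k = 6 whatever the enrolment pattern. If only the timing of the evaluation matters, a patient who started at least 16 days before the sixth has reached day 37 when the sixth completes day 21, so k counts only the later starters.

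**The case against.** The best reply is that the plan sets no calendar day. It says after, or upon, completion of cycle 1, and enrolment reopens only when the DLT evaluation is complete. An evaluation against seven criteria is arguably incomplete while one is open, and a reading that makes a listed criterion impossible to score is not the natural one. A team could take the toxicity as arising in cycle 1, judge criterion 5 by its consequence, and wait.

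That stands in part. A reader might infer that the decision is fixed at day 21, or that a patient on hold must be scored DLT-free; the document says neither. But nothing requires the team to wait, and the alternative reading has to set aside the stated window. If cycle 1 were instead taken to last until cycle 2 starts, that would conflict with the 21-day cycle and could leave its completion open for as long as the 12-week delay allowance.

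Three further points limit the size. The 83% and 90% figures need criterion 5 to go unscored in all six patients; staggered starts would leave fewer. Grade 2 toxicity does not clearly block cycle 2, so the share caught only by criterion 5 may be below 10–15%. Other safeguards remain: the same delay triggers a vorinostat dose modification for that patient (5.2.1.3), the study team reviews adverse events weekly (10.6), a data and safety monitoring committee oversees the study (10.5), and the incidence or severity of adverse reactions can end the trial (5.10). These protect patients but do not correct the count.

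**Conclusion.** The inconsistency is real. The stated window and decision time, followed literally, remove a listed DLT from the count that selects the phase II regimen, and the bias can only favour the starting regimen. Under the assumed rates, one or two unobservable patients raise the chance of keeping that regimen by about 1 to 10 percentage points. The worst case adds about 7 to 29 points (83% to 90%; 54% to 83%). The direction and the day-37 arithmetic rest on the document; the sizes rest on DLT rates that it does not give.

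A reader might also infer that the whole primary safety objective is undermined. The document does not support that. Sections 8.1 and 8.2 summarise toxicity in all enrolled patients, run-in and expansion, so an event missed by the run-in count can still enter the safety analysis. What is exposed is the run-in decision.

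**What to change.** Reconcile sections 2.1.1, 2.1.1.1 and 2.1.2 so that the observation period covers every listed criterion:
- In 2.1.1 and 2.1.2, state that the formal evaluation is complete only when each of the six patients has started cycle 2, has already had a DLT, or has been followed long enough to confirm or rule out a cycle 2 delay of more than 2 weeks.
- In 2.1.1.1, word the window as cycle 1 and, for criterion 5, the delay before cycle 2.

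The DLT list, the 2-of-6 threshold and both regimens stay as they are. Sections 5.2.1.2 and 5.2.1.5 should also be reconciled on whether Grade 2 toxicity holds the next cycle, since that determines how often criterion 5 comes into play; which rule applies is a clinical matter for the investigators.

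The cost is a wording amendment and possibly a longer pause. Enrolment is already closed at this point and may stay closed for up to about two more weeks, and only if a run-in patient is on hold when cycle 2 is due.

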2.1.2. Phase II expansion

After the first 6 patients have been assessed for DLTs upon completion of cycle 1 of treatment, and the appropriate vorinostat dose and MK-3475 dosing interval determined for phase II expansion, additional patients will be enrolled with RMHNSCC (Cohort 1) and RMSCG (Cohort 2) to total 35 patients in each cohort. Patients enrolled in the phase I and II portions will be used to assess the safety and efficacy outcomes of interest in each cohort.

Patients will be evaluated every 9 weeks $(63 \pm 7 \text{ days})$ with radiographic imaging to assess response to treatment. All imaging will be assessed using Response Evaluation Criteria in Solid Tumors (RECIST) 1.1 Patients will also be assessed by immune response criteria (IrRC – Appendix) for determination of overall response rate (ORR) and progression-free survival (PFS). Adverse events will be monitored throughout the trial and graded in severity according to the guidelines outlined in the NCI Common Terminology Criteria for Adverse Events (CTCAE) version 4.0.

Treatment with MK-3475 and vorinostat will continue until two years of therapy have been administered, or until

- 1. Documented disease progression (investigators may elect to continue MK-3475 treatment beyond progression in specific circumstances, unacceptable adverse event(s)
- 2. Intercurrent illness that prevents further administration of treatment
- 3. Investigator's decision to withdraw the subject
- 4. Subject withdraws consent,
- 5. Pregnancy of the subject,
- 6. Non-compliance with trial treatment or procedure requirements, or administrative reasons.

MK-3475 and vorinostat treated subjects who attain an investigator-determined confirmed complete response (CR) per RECIST 1.1 and IrRC may consider stopping trial treatment. Patients with a CR may continue on therapy for up to 2 cycles until a confirmatory scan is undertaken. If patients upon a confirmed CR progress they may continue therapy on a second course of therapy the combination until toxicity, progression. These subjects will be eligible for re-treatment for up to one year with MK-3475 and vorinostat after they have experienced radiographic disease progression at the discretion of the investigator according to the criteria in Section 5.1.4; this re-treatment will be the Second Course Phase. Response or progression in the Second Course Phase will not count towards the ORR and PFS of the primary endpoint in this trial.

After the end of treatment, each patient will be followed for a minimum of 30 days for adverse event monitoring (serious adverse events will be collected for up to 90 days after the end of treatment). Subjects will have post-treatment follow-up for disease status until death, withdrawing consent, or becoming lost to follow-up.

Participation in this trial will be dependent upon supplying tumor tissue from either a newly obtained formalin-fixed specimen, or an older formalin-fixed, paraffin-embedded specimen from locations not radiated prior to biopsy. Newly obtained formalin-fixed specimens are strongly encouraged unless clinically contraindicated as deemed by the treating physician. If new scientific data emerge that indicate that an existing biopsy or surgical specimen is suboptimal for identification of patients, only new biopsies will be acceptable for determination of PD-L1 status. The specimen will be evaluated at a central laboratory facility for expression status of PD-L1 in a prospective manner.

2.1.2.1 Safety assessments during the Phase II expansion

This investigator initiated study will be under the oversight of the Fred Hutchinson/University of Washington Cancer Consortium IRB and Data and Safety Monitoring committee. The investigators are ultimately responsible for monitoring the safety of patients who have entered this study and for alerting the Consortium IRB to any event that seems unusual in accordance with IRB policy. The investigator is responsible for the appropriate medical care of patients during the study. The investigator remains responsible to follow, through an appropriate health care option, adverse events that are serious or that caused the patient to discontinue before completing the study. The patient should be followed until the event resolves or stabilizes. Frequency of follow-up is left to the discretion of the investigator.

Safety measurements that will be used in the study include physical examinations and clinical laboratory tests (hematology and blood chemistries). The adverse event will be graded for toxicity using the NCI CTC version 4.0. Toxicity assessment will occur at the start of each cycle, or more frequently if clinically indicated. Any adverse events leading to a treatment interruption or dose reduction along with all adverse events that are grade 3 and higher will be recorded in the CRF. Adverse Events that meet Merck's definition of Event of Clinical Interest (refer to the Pembrolizumab ECI guidance document) will also be recorded.

The criteria for dose de-escalation for adverse events are outlined in Section 5.2. Any patient who requires two dose modifications or de-escalations will be taken off study.

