5.2.1.2 Dose Modifications for MK-3475 and Vorinostat

Toxicity will be graded using Common Terminology Criteria for Adverse Events (CTCAE version 4.0). The protocol will change to CTCAE version 5.0 if is published within the course of the trial.

Because it there may be overlap in the toxicities of both agents, and difficulty in attributing toxicity to either agent, patients experiencing any Grade 3 toxicity (except those outlined in Table 3.1 and Section 5.2.1.4) or any Grade 4 toxicity will have *both MK-3475 and vorinostat held until improvement of the adverse event to Grade 1 or baseline*.

Toxicity that requires more than two dose reductions or modifications of vorinostat will lead to discontinuation of the patient from the treatment phase of the study. *Patients are not permitted to continue on vorinostat or MK-3475 dosing alone.* In addition, no dose re-escalations are allowed during the study period unless toxicities are resolved to grade 1. Justification will be recorded in the source documents

Before initiation of subsequent cycles, each patient will be evaluated for possible toxicities that may have occurred after the previous treatment. All Grade 3 or 4 toxicities

(except those specified in Table 3.1 and Section 5.2.1.4) should resolve to Grade 1 or baseline before re-initiation of study treatment. Dose modification will be made based on the toxicity with the greatest severity.

Toxicity	Grade	Hold Treatment (Y/N)	Timing for restarting treatment	Dose/Schedule for restarting treatment	Discontinue Subject (after consultation with Sponsor)
Hematological Toxicity	1, 2	No	N/A	N/A	N/A
	3* *Excluding Grade 3 neutropenia, anemia, and thrombocytopenia See Section 5.2.1.4)	Yes	Toxicity resolves to Grade 0-1 or baseline	May increase the dosing interval by 1 week	Toxicity does not resolve within 12 weeks of last infusion Permanent discontinuation should be
	4	Yes	Toxicity resolves to Grade 0-1 or baseline	May increase the dosing interval by 1 week	considered for any severe or life-threatening event
Non-hematological toxicity	1	No	N/A	N/A	N/A

Toxicity	Grade	Hold Treatment (Y/N)	Timing for restarting treatment	Dose/Schedule for restarting treatment	Discontinue Subject (after consultation with Sponsor)

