 Note: Exception to be treated similar to grade 1 toxicity Grade 2 alopecia Grade 2 fatigue For additional information regarding Adverse Events with a potential Immune-Etiology reference Section 5.6.1.1. and Appendix 12.8 	2	Consider withholding for persistent symptoms	Toxicity resolves to Grade 0-1 or baseline	Clinical AE resolves within 4 weeks: Same dose and schedule (reference Section 5.6.1.2 for recommendations regarding pneumonitis) Clinical AE does not resolve within 4 weeks: May increase the dosing interval by 1 week for each occurrence	Toxicity does not resolve within 12 weeks of last infusion
	3, 4	Yes	Toxicity resolves to Grade 0-1 or baseline	May increase the dosing interval by 1 week for each occurrence	Toxicity does not resolve within 12 weeks of last infusion Permanent discontinuation should be considered for any severe or life-threatening event

In case toxicity does not resolve to Grade 0-1 within 12 weeks after last infusion, trial treatment should be discontinued. With investigator and Sponsor agreement, subjects with a laboratory adverse event still at Grade 2 after 12 weeks may continue treatment in the trial only if asymptomatic and controlled. For information on the management of adverse events, see Section 5.6.1.

Subjects who experience a recurrence of the same severe or life-threatening event at the same grade or greater with re-challenge of MK-3475 should be discontinued from trial treatment.

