5.2.1.3. Dose Modifications for Vorinostat

Because there may be overlap between vorinostat and MK-3475 toxicities, patients experiencing any Grade 3 toxicity (except those outlined in Table 3.1 and Section 5.2.1.4) or any Grade 4 toxicity will have *both MK-3475 and vorinostat held until improvement of the adverse event to Grade 1 or baseline.*

The following table describes vorinostat dose levels for patients receiving MK-3475 and vorinostat combination *for the phase I portion of the study*, This table will also be used in the Phase II portion of the *study if the Vorinostat dose is determined to be 400mg*.

Starting Dose	1st dose reduction	2nd dose reduction	3rd Dose Reduction
Vorinostat	Vorinostat	Vorinostat	Discontinue therapy
4 capsules – 400 mg	3 capsules – 300 mg	2 capsules – 200 mg	
OR	OR	OR	
8mL of 50mg/ml	6mL of 50mg/mL	4mL of 50mg/mL	
suspension	suspension	suspension	
5 out of 7 days	5 out of 7 days	5 out of 7 days	

Table 3.2 Dose Reduction Steps for Vorinostat-Specific Related Toxicities

If the phase I lead in portion determines that the phase II vorinostat dose is 300mg daily the following table will be used for vorinostat dose modifications.

Starting Dose	1st dose reduction	2nd dose reduction	3rd Dose Reduction
Vorinostat	Vorinostat	Vorinostat	Discontinue therapy
3 capsules – 300 mg	2 capsules – 200 mg	1 capsules – 100 mg	
OR	OR	OR	
6mL of 50mg/mL	4mL of 50mg/mL	2mL of 50mg/mL	
suspension	suspension	solution	
5 out of 7 days	5 out of 7 days	5 out of 7 days	

Any of the following will necessitate vorinostat dose modification:

1. Grade 4 non-hematologic toxicity (not laboratory)

2. Grade 3 non-hematologic toxicity (not laboratory) lasting >3 days despite optimal supportive care.

- 3. Any Grade 3 or Grade 4 non-hematologic laboratory value if:
 - Medical intervention is required to treat the patient, or
 - The abnormality leads to hospitalization

4. Grade 3 or Grade 4 febrile neutropenia:

Grade 3 is defined as ANC <1000/mm3 with a single temperature of >38.3 degrees C (101 degrees F) or a sustained temperature of \geq 38 degrees C (100.4 degrees F) for more than one hour

Grade 4 is defined as ANC <1000/mm3 with a single temperature of >38.3 degrees C (101 degrees F) or a sustained temperature of \geq 38 degrees C (100.4 degrees F) for more than one hour, with life-threatening consequences and urgent intervention indicated.

- 5. Prolonged delay (>2 weeks) in initiating cycle 2 due to treatment-related toxicity

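### Section 2.1.2.1 takes a Phase II patient off study at two dose modifications, while the vorinostat tables in 5.2.1.3 give a second-reduction level and stop only at the third

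*Combined protocol and SAP*

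**What the plan says.** Section 2.1.2.1 (safety during the Phase II expansion) sends the reader elsewhere for the criteria: "The criteria for dose de-escalation for adverse events are outlined in Section 5.2". Its next sentence sets a removal rule of its own: "Any patient who requires two dose modifications or de-escalations will be taken off study". It names no drug.

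Section 5.2.1.2 uses a different count, limited to vorinostat: "Toxicity that requires more than two dose reductions or modifications of vorinostat will lead to discontinuation of the patient from the treatment phase".

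Section 5.2.1.3 gives two vorinostat tables. For the one starting at 400 mg, the text says "This table will also be used in the Phase II portion of the" study when the dose is set at 400 mg. For the other: "If the phase I lead in portion determines that the phase II vorinostat dose is 300mg daily the following table will be used". Each table assigns a dose to the first and second reductions, and each places the instruction to discontinue under the column headed "3rd Dose Reduction".

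Two further provisions of Section 5.2.1.2 bear on the count. For MK-3475, Table 3.1 responds to Grade 3 or 4 non-hematological toxicity by schedule: "May increase the dosing interval by 1 week for each occurrence". Separately, treatment is to stop for this group: "Subjects who experience a recurrence of the same severe or life-threatening event at the same grade or greater" on re-challenge with MK-3475.

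**The concern.** A removal rule has to give one answer for one patient. Here the count in 2.1.2.1 is reached one step before the tables in 5.2.1.3 stop therapy, so the second-reduction column could not be used for vorinostat reductions in Phase II. Whichever section a site follows at that step, it departs from the other.

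The choice determines whether a patient stays on the combination at a lower vorinostat dose or comes off. That affects exposure, and through it the toxicities that can be observed, in a trial whose primary objective (Section 3.1) is safety and tolerability.

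Three points of wording make the count harder to apply:

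- **What counts.** Section 2.1.2.1 names no drug and 5.2.1.2 counts vorinostat only, while 5.2.1.4.2 (diarrhea) and 5.9 speak of modifying both drugs. Whether an MK-3475 interval extension counts under 2.1.2.1 is not stated.
- **What follows.** Section 2.1.2.1 ends study participation, whereas 5.2.1.2 ends the treatment phase.
- **Who is covered.** Section 2.1.2.1 is headed for the expansion. The six run-in patients have the second-reduction level under 5.2.1.3, and 5.9 allows them modification with continued therapy after a DLT. Whether the two-modification rule reaches them is not stated.

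**Working it through.** The plan has no computed figure on this point to reproduce. The check sets the rules side by side and works out which doses each leaves reachable.

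**Step 1. The rules, by number of vorinostat reductions needed**

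| Reductions needed | 2.1.2.1 (Phase II) | 5.2.1.2 | 5.2.1.3, 400 mg start | 5.2.1.3, 300 mg start |
|---|---|---|---|---|
| 1 | continue | no stop required | 300 mg | 200 mg |
| 2 | off study | no stop required | 200 mg | 100 mg |
| 3 | already off | leave treatment phase | discontinue | discontinue |

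The conflict is in the second row. Section 5.2.1.2 alone does not forbid an earlier stop, so it supports the point without proving it. The direct clash is between 2.1.2.1 and the tables in 5.2.1.3, which assign a dose to the very step at which 2.1.2.1 removes the patient. One table or the other applies in Phase II whichever dose the run-in selects, so the clash does not depend on that outcome.

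**Step 2. Can a patient reach that row without being stopped for another reason?** Take two different events. Grade 4 thrombocytopenia makes a dose adjustment mandatory (5.2.1.4.1). Later, Grade 3 vomiting that lasts more than 72 hours despite supportive care leads to a further stepwise reduction (5.2.1.4.2). If both resolve in time and the investigator does not stop treatment at discretion, the patient moves to the second-reduction level under 5.2.1.3 and off study under 2.1.2.1. Recurrence of the same severe event at the same or a higher grade on re-challenge is outside the conflict, because 5.2.1.2 already stops treatment there.

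**Step 3. Lowest vorinostat dose reachable on treatment.** Weekly dose = 5 days × daily dose, using the levels in the 5.2.1.3 tables.

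| Start | Starting weekly dose | Lowest under 2.1.2.1 (first reduction) | Lowest under 5.2.1.3 (second reduction) |
|---|---|---|---|
| 400 mg | 5 × 400 = 2,000 mg | 5 × 300 = 1,500 mg (300/400 = 75%) | 5 × 200 = 1,000 mg (200/400 = 50%) |
| 300 mg | 5 × 300 = 1,500 mg | 5 × 200 = 1,000 mg (200/300 = 67%) | 5 × 100 = 500 mg (100/300 = 33%) |

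**Step 4. Patients to whom the rule in 2.1.2.1 clearly applies.** The plan has 35 + 35 = 70 patients, of whom the first six form the run-in. That leaves 70 − 6 = 64, before any run-in replacement under 5.9. This counts patients under the rule's heading. It does not estimate how many would need a second modification, and the documents give no rate from which to derive that.

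**The case against.** The best defense is that the operating text lies in Section 5.2 and that 2.1.2.1 is only an overview. Section 2.1.2.1 itself points to 5.2 for de-escalation criteria. The discontinuation list in 5.8 cites 5.2.1.2 for unacceptable adverse experiences and does not repeat a two-modification rule, and 5.9 also cites 5.2.1.2. A careful site might therefore follow the tables. This makes one reading more natural but does not settle the matter. The pointer covers criteria for de-escalation, and the removal count follows it as a separate, unqualified instruction. No clause gives either section precedence.

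A second objection concerns consequence, and much of it stands. Section 8.2 summarizes toxicities as numbers and percentages of patients by type, not by dose level, and names no discontinuation endpoint. The Phase II dose decision rests on Cycle 1 DLTs in the first six patients, not on this count. The dose figures above restate the tables and do not measure impact.

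The difference between leaving the study and leaving the treatment phase is also weak evidence on its own, since the protocol uses such terms loosely. Section 5.8, for example, discontinues subjects from the trial and then provides follow-up for them. Sections 2.1.2, 5.8, 7.1.5.4 and 7.1.5.4.1 already provide disease or survival follow-up after treatment, so loss of progression or survival data is not claimed.

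**Conclusion.** The concern holds and should be corrected. For a Phase II patient who needs exactly two vorinostat reductions and is not otherwise required to stop, the protocol gives opposite instructions at either possible Phase II dose. The difference is one full dose level: a weekly floor of 1,500 against 1,000 mg from a 400 mg start, or 1,000 against 500 mg from a 300 mg start.

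The importance rests on a contradictory stopping rule for individual patients in a trial whose primary objective is safety and tolerability. It does not rest on any change to alpha, power or sample size, because there is none. The number of patients affected is unknown. The conclusion assumes only that two vorinostat reductions count as two modifications under 2.1.2.1, which its wording supports. If MK-3475 interval extensions count as well, the mismatch is wider. No view is taken on which count is clinically right.

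**What to change.** Reconcile 2.1.2.1, 5.2.1.2 and 5.2.1.3, and check Table 3.1, 5.2.1.4.1 and 5.2.1.4.2 against the result. The amended text should state:

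- one count at which the patient stops;
- one definition of a countable modification, including whether an MK-3475 interval extension counts;
- one consequence, in the same words in each place;
- whether the rule covers the six run-in patients.

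A short pointer in 2.1.2.1 to the existing follow-up provisions would remove doubt about patients stopped under it; they need not be restated. Which count and which consequence to adopt is a clinical decision for the sponsor.

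The cost is a wording amendment, with no new data, patients or analyses.
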